6.7 IMMUNOGENICITY ANALYSES

The immunogenicity analyses for atezolizumab will include patients with any ADA result, with patients grouped by cohort.

The numbers and proportions of ADA-positive patients and ADA-negative patients during both the treatment and follow-up periods will be summarized by cohort. Patients are considered to be ADA positive if they are ADA negative or are missing data at baseline but develop an ADA response following study drug administration (treatment-induced ADA response), or if they are ADA positive at baseline and the titer of one or more post-baseline samples is at least 4-fold greater (i.e., ≥ 0.60 titer unit) than the titer of the baseline sample (treatment-enhanced ADA response). Patients are considered to be ADA negative if they are ADA negative or are missing data at baseline and all post-baseline samples are negative, or if they are ADA positive at baseline but do not have any post-baseline samples with a titer that is at least 4-fold greater than the titer of the baseline sample (treatment unaffected).

The relationship between ADA status and safety, efficacy, PK, and biomarker endpoints may be analyzed and reported descriptively in subgroup analyses.

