
 To evaluate the immune response to atezolizumab in previously untreated patients and in patients who have progressed on previous anti-PD-1 therapy 	
 Incidence of ADAs to atezolizumab during the study relative to the prevalence of ADAs at baseline
Exploratory Immunogenicity Objective	

 To evaluate potential effects of ADAs 	
 Relationship between ADA status and efficacy, safety, or PK endpoints
Exploratory Biomarker Objectives	

 Mechanisms of resistance to anti-PD-1 in Cohorts A and B or anti-PD-L1 in Cohort C Cobimetinib effect on tumor immune contexture 	
 TIL distribution, CD8, PD-L1, and stromal markers (TBD) by IHC Immune-signatures and stromal signature by RNA sequencing RAS, NF1 mutations, tMB and TCR repertoires by DNA sequencing

ADA=anti-drug antibody; anti-PD-1 = anti-programmed death-1; CR=complete response; DOR=duration of response; DCR=disease control rate; IHC= immunohistochemistry; IRC=*independent review committee*; NCI CTCAE=National Cancer Institute Common Terminology Adverse Events; OR=objective response; ORR=objective response rate; OS=overall survival; PD-L1 = programmed death–ligand 1; PK= pharmacokinetic; PFS=progression-free survival; PR=partial response; RECIST=Response Evaluation Criteria in Solid Tumors; SD=stable disease; TBD=to be determined; TIL =tumor-infiltrating lymphocyte; TCR=T-cell receptor; tMB=tumor mutation burden; WT=wild type.

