- ^a Results of standard-of-care tests or examinations performed before obtaining informed consent and within 35 days before Day 1 may be used; such tests do not need to be repeated for screening. *BRAF*^{V600} status must be known before performing study-specific screening assessments. The 35-day window begins at the time of the first standard-of-care screening assessment or the first study-specific screening assessment after the *BRAF*^{V600} mutation test result is available, whichever is earlier. Test results should be reviewed before study treatment is given.
- ^b Patients who discontinue study drug will return to the clinic for a treatment discontinuation visit at 30 (± 3) days. The visit at which response assessment shows PD may be used as the study discontinuation visit.
- ^c Visit not specified by the protocol. Assessments (possibly including PK sample collection) should be performed as clinically indicated.
- ^d Required follow-up information will be collected via telephone calls and/or clinic visits every 3 months until death, loss to follow-up, or study termination by the Sponsor. PK/ADA sample is required 120 days \pm 30 days after last atezolizumab infusion
- ^e Informed consent must be documented before any study-specific screening procedure is performed and may be obtained up to 35 days before initiation of study treatment.
- ^f Includes respiratory rate, heart rate, and systolic and diastolic blood pressure (after patient has been in a seated position for 5 minutes) and temperature (oral or tympanic); resting oxygen saturation may be measured at screening. Record abnormalities observed at baseline on the General Medical History and Baseline Conditions eCRF. At subsequent visits, record new or worsened clinically significant abnormalities on the Adverse Event eCRF.
- ^g Vital signs at the first atezolizumab infusion will be collected within 60 min before the infusion, every 15 (± 5) min during the atezolizumab infusion, and 30 (± 10) min after the infusion. For subsequent infusions, vital signs will be collected within 60 min before infusion and during the infusion (if clinically indicated or if symptoms occurred in the prior infusion), and 30 (± 10) min after the infusion.

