Appendix 2 Schedule of Pharmacokinetic, Immunogenicity, and Biomarker Samples

Cohort A

Visit	Timepoint	Sample Type(s)
Cycle 1, Day 1	Prior to the first infusion	Atezolizumab PK and ADA (serum)
	30 (\pm 10) minutes following the end of atezolizumab infusion	Atezolizumab PK (serum)
	2–4 hours after the cobimetinib dose	Cobimetinib PK (plasma)
Cycle 1, Day 15	Prior to cobimetinib dose 2–4 hours post cobimetinib dose	Cobimetinib PK (plasma)
Cycles 2, 3, 4, 8, 12, and 16	Prior to the first infusion	Atezolizumab PK and ADA (serum)
Cycles 1 and 2, Day 1 At time of tumor assessments (preferably within 3 days) At disease progression	Predose	Biomarker (plasma, PBMC)
Treatment discontinuation visit ^a	At visit	Atezolizumab PK and ADA (serum) Biomarker (plasma, PBMC) ^b
120 days \pm 30 days after last atezolizumab infusion	At visit	Atezolizumab PK and ADA (serum)

ADA=anti-drug antibody; PBMC=peripheral blood mononuclear cell; PK=pharmacokinetic.

Note: Except for Day 1 of Cycle 1, all other study visits and assessments during the treatment period should be performed within \pm 3 days of the scheduled date. Study assessments may be delayed or moved ahead of the window to accommodate holidays, vacations, and unforeseen delays.

^a Patients who discontinue study drug will return to the clinic for a treatment discontinuation visit 30 (\pm 3) days after the last dose of study drug. The visit at which response assessment shows progressive disease may be used as the treatment discontinuation visit.

^b At confirmed disease progression, lack of clinical benefit, or at treatment discontinuation.

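### Section 6.7 does not require a post-baseline result for the ADA proportions, so patients with only a baseline sample dilute treatment-emergent ADA incidence, probably by little

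*Combined protocol and SAP*

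**What the plan says.** The immunogenicity endpoint in Section 2 (Table 1, and the synopsis) is "Incidence of ADAs to atezolizumab during the study relative to the prevalence of ADAs at baseline". Section 6.7 gives the analysis set in one sentence, "The immunogenicity analyses for atezolizumab will include patients with any ADA result, with patients grouped by cohort", and then the summary: "The numbers and proportions of ADA-positive patients and ADA-negative patients during both the treatment and follow-up periods will be summarized by cohort".

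There are two ways to be ADA positive. One is a response after study drug in a patient who was negative or had no data at baseline. The other is a post-baseline titer at least 4-fold above a positive baseline.

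There are also two ways to be ADA negative. For patients negative or without data at baseline, "Patients are considered to be ADA negative if they are ADA negative or are missing data at baseline and all post-baseline samples are negative". For baseline-positive patients, the classification is negative "if they are ADA positive at baseline but do not have any post-baseline samples with a titer that is at least 4-fold greater" than at baseline, which the plan labels treatment unaffected.

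Appendix 2 schedules ADA samples before the first atezolizumab infusion, before the first infusion of "Cycles 2, 3, 4, 8, 12, and 16", at the treatment discontinuation visit, and 120 (±30) days after the last infusion.

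**The concern.** The endpoint sets two quantities side by side: how many patients carried ADA at baseline, and how many developed or boosted ADA on study. The second can be observed only in someone sampled after treatment began. A set open to any ADA result suits the immunogenicity section as a whole, but it is too wide as the denominator for incidence. Patients who leave before any later draw add to the denominator and can never add to the numerator.

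At stake is a modest understatement of a stated endpoint. There is also some blurring of the exploratory summaries by ADA status, if baseline-only patients are placed in the ADA-negative group.

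**Working it through.** **1. Status of a patient with only a baseline sample, under the text of Section 6.7**

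- *Baseline positive.* Such a patient does "do not have any post-baseline samples with a titer that is at least 4-fold greater than the titer of the baseline sample", because there are no post-baseline samples. The negative definition is met literally.
- *Baseline negative.* The condition that all post-baseline samples be negative holds only vacuously. The patient is either negative on that reading or unclassified but still in the stated set.
- *Positive.* Neither route is open, since both need a post-baseline result.

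Whether the baseline-negative patient is called negative or left unclassified within the set, the proportion positive has the same value. The dilution goes away only if the proportions use a narrower denominator than the one stated, and no section says so.

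**2. Formula**

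Let x be the number ADA positive, e the number with at least one post-baseline result, and b the number with a baseline result only. Write p = x/e and f = b/(e + b).

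Reported proportion = x/(e + b) = p(1 − f). Shortfall = p·f.

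The shortfall is never negative, so the bias is downward whenever b and x are above zero.

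**3. Inputs**

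Planned cohort sizes (Section 6.1) are about 90 in A, 12 in B and 50 in C. The documents give no value for f or p. The ranges f = 2–15% and p = 10–40% are assumptions. The plan states no ADA rate or precision to reproduce. The one figure in Section 6.7 that can be checked, the 0.60 titer unit for a 4-fold rise, agrees with log10(4) = 0.602.

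**4. Shortfall p·f, in percentage points**

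| f | p = 10% | p = 20% | p = 30% | p = 40% |
|---|---|---|---|---|
| 2% | 0.2 | 0.4 | 0.6 | 0.8 |
| 5% | 0.5 | 1.0 | 1.5 | 2.0 |
| 10% | 1.0 | 2.0 | 3.0 | 4.0 |
| 15% | 1.5 | 3.0 | 4.5 | 6.0 |

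**5. The same in whole patients** (assumed counts near p = 30%, every enrolled patient having some ADA result)

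| Cohort | Baseline only | Positive | Whole set | Post-baseline result required |
|---|---|---|---|---|
| A (90) | 4 | 26 | 26/90 = 28.9% | 26/86 = 30.2% |
| A (90) | 9 | 24 | 24/90 = 26.7% | 24/81 = 29.6% |
| A (90) | 14 | 23 | 23/90 = 25.6% | 23/76 = 30.3% |
| C (50) | 2 | 14 | 14/50 = 28.0% | 14/48 = 29.2% |
| C (50) | 5 | 14 | 14/50 = 28.0% | 14/45 = 31.1% |
| B (12) | 1 | 3 | 3/12 = 25.0% | 3/11 = 27.3% |

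Rounding to whole patients can push the top of the range slightly above 6 points. In Cohort C, 8 baseline-only patients (16%) with 17 positive give 34.0% against 17/42 = 40.5%.

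**6. Scale against sampling error**

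The exact 95% interval for 26/86 is 20.8% to 41.1%. The 1.3-point shift in that row lies well inside it.

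**7. How a baseline-only patient arises**

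With 28-day cycles the first post-baseline ADA draw in Cohort A is on about Day 29. With 21-day cycles in Cohort C it is on about Day 22. In Cohort B the baseline draw is on Cycle 1 Day 15 and the next is two weeks later. To be baseline-only, a patient must miss that draw, the discontinuation-visit draw and the 120-day draw. That points mainly to very early death or withdrawal of consent, after which Section 4.5.1 allows no follow-up.

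**The case against.** The best defense is that Section 6.7 omits a clarification and does not choose a wrong rule. One inclusion sentence has to cover prevalence, incidence and patients with no baseline sample, so it is broad by design and need not be the incidence denominator. Status during the treatment and follow-up periods, and the label treatment unaffected, arguably presuppose a sample from those periods. This stands in part: the text never says that all baseline-only patients are negative, and a reader who infers that goes too far. It is literal only for the baseline-positive ones. But the stated set is the only set, and leaving a patient unclassified within it still dilutes the positive proportion.

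The second objection is size. The schedule offers several later draws, including two after stopping, and Section 4.1.1.4 requires ECOG 0–1 and a life expectancy of at least 18 weeks. Baseline-only patients should be uncommon. This stands, and it is why the low end of the range is the more plausible.

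The third concerns the ADA-status comparisons. A reader might infer that the rule seriously distorts ADA versus efficacy by placing poor-prognosis drop-outs in the negative group, and that requiring a post-baseline sample would cure it. The documents do not support either step. They give no outcome data for early drop-outs, and Section 6.7 makes these comparisons optional and descriptive. Requiring a later sample also conditions on staying in the study long enough to give one.

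**Conclusion.** The point holds in a limited form. As written, the set used for the ADA proportions is wider than the group in whom treatment-emergent ADA can be observed, and incidence is understated by the factor (1 − f). The direction follows from the definitions. The size rests wholly on assumed values: about 0.2 to 6 percentage points for f of 2–15% and incidence of 10–40%, probably near the low end given the sampling schedule. The analysis is descriptive, no formal testing is planned (Section 6.1), and the co-primary endpoints are untouched. The documents do not support a claim of material bias in the trial's conclusions, or any particular ADA rate or baseline-only share. This is a minor improvement to the plan.

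**What to change.** Amend Section 6.7 to name two denominators and one count:

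- baseline prevalence, among patients with a baseline ADA result;
- treatment-emergent incidence, and any summaries by ADA status, among patients treated with atezolizumab who have at least one post-baseline ADA result;
- the number of patients, by cohort, with baseline data only.

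ADA status will still depend on how long a patient was followed and sampled, so the summaries of ADA against efficacy should stay descriptive and be labelled so. The cost is a sentence or two, with no new samples or visits.

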Appendix 2 Schedule of Pharmacokinetic, Immunogenicity, and Biomarker Samples (cont.)

Cohort C

Visit	Timepoint	Sample Type(s)
Cycle 1, Day 1	Prior to the first infusion	Atezolizumab PK and ADA (serum)
	30 (\pm 10) minutes following the end of atezolizumab infusion	Atezolizumab PK (serum)
Cycles 2, 3, 4, 8, 12, and 16	Prior to the first infusion	Atezolizumab PK and ADA (serum)
Cycles 1 and 2, Day 1 At time of tumor assessments (preferably within 3 days) At disease progression	Predose	Biomarker (plasma, PBMC)
Treatment discontinuation visit ^a	At visit	Atezolizumab PK and ADA (serum) Biomarker (plasma, PBMC) ^b
120 days \pm 30 days after last atezolizumab infusion	At visit	Atezolizumab PK and ADA (serum)

ADA = anti-drug antibody; PBMC = peripheral blood mononuclear cell; PK = pharmacokinetic.

Note: Except for Day 1 of Cycle 1, all other study visits and assessments during the treatment period should be performed within \pm 3 days of the scheduled date. Study assessments may be delayed or moved ahead of the window to accommodate holidays, vacations, and unforeseen delays.

^a Patients who discontinue study drug will return to the clinic for a treatment discontinuation visit 30 (\pm 3) days after the last dose of study drug. The visit at which response assessment shows progressive disease may be used as the treatment discontinuation visit.

^b At confirmed disease progression, lack of clinical benefit, or at treatment discontinuation.

Appendix 3

Response Evaluation Criteria in Solid Tumors: Modified Excerpt from Original Publication

Selected sections from the Response Evaluation Criteria in Solid Tumors (RECIST), Version 1.1¹ are presented below, with slight modifications and the addition of explanatory text as needed for clarity.²

MEASURABILITY OF TUMOR AT BASELINE

DEFINITIONS

At baseline, tumor lesions/lymph nodes will be categorized measurable or non-measurable as follows:

Measurable Tumor Lesions

Tumor Lesions. Tumor lesions must be accurately measured in at least one dimension (longest diameter in the plane of measurement is to be recorded) with a minimum size of:

- 10 mm by computed tomography (CT) or magnetic resonance imaging (MRI) scan (CT/MRI scan slice thickness/interval no greater than 5 mm)
- 10-mm caliper measurement by clinical examination (lesions that cannot be accurately measured with calipers should be recorded as non-measurable)
- 20 mm by chest X-ray

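### ADA status taken over the whole study is allowed into efficacy subgroups; with no true ADA effect this favours ADA-positive patients on average

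*Combined protocol and SAP*

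**What the plan says.** Section 6.7 sets ADA status as follows.

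- **Positive:** patients negative or missing at baseline who "develop an ADA response following study drug administration", or patients positive at baseline for whom "the titer of one or more post-baseline samples is at least 4-fold greater" than the baseline titer. Neither rule has a time limit.
- **Negative:** patients who are "ADA negative or are missing data at baseline and all post-baseline samples are negative", or who are positive at baseline without a 4-fold rise.
- **Window:** the numbers positive and negative "during both the treatment and follow-up periods will be summarized by cohort".
- **Population:** "The immunogenicity analyses for atezolizumab will include patients with any ADA result". No post-baseline sample is required.
- **Use:** "The relationship between ADA status and safety, efficacy, PK, and biomarker endpoints may be analyzed and reported descriptively in subgroup analyses." No landmark, time-dependent method or early-sample rule is given.

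Table 1 (Section 2) lists "Relationship between ADA status and efficacy, safety, or PK endpoints" as the endpoint of an exploratory immunogenicity objective. Appendix 2 schedules post-baseline ADA samples at "Cycles 2, 3, 4, 8, 12, and 16", at the discontinuation visit and about 120 days after the last infusion. Section 3.1.2 lets atezolizumab continue until toxicity or loss of benefit. Section 6.4.2 counts PFS and OS from Cycle 1, Day 1.

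**The concern.** The grouping variable is built from events after time zero, and the chance of observing those events grows with time on treatment. A patient who does well gives more samples over a longer period. A patient who fails early gives few. A patient with only a baseline sample is admitted to the analysis and, read literally, meets the negative definition if that sample was negative. Comparing PFS, OS or response between these groups from Cycle 1, Day 1 is the usual setting for immortal-time bias.

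The question behind the Table 1 endpoint is whether antibodies reduce benefit. A bias that favours ADA-positive patients works against detecting that. For illustration only: a true hazard ratio of 1.25 multiplied by a bias factor of 0.80 reads as 1.25 × 0.80 = 1.00.

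**Working it through.** The plan gives no expected ADA incidence, onset time or effect size, so there is no planned figure to reproduce. The check has four steps.

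**1. Sampling opportunity.** Cycle k, Day 1 falls at week (k − 1) × cycle length. Section 3.1 gives 28-day cycles for Cohorts A and B and 21-day cycles for Cohort C.

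- Cohort A: weeks 4, 8, 12, 28, 44, 60.
- Cohort C: weeks 3, 6, 9, 21, 33, 45.
- Treatment stops at week 8 with no Cycle 3 dose in Cohort A: 1 on-treatment sample in A, 2 in C. With the discontinuation and 120-day samples, 3 and 4.
- Treatment for 52 weeks: 5 on-treatment samples in A, 6 in C. With the two later samples, 7 and 8.

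**2. Simulation with no ADA effect.** There were 300,000 patients per scenario, classified by the Section 6.7 rule. A one-covariate Cox model compared ADA positive with ADA negative from Cycle 1, Day 1.

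- From the documents: sampling cycles (Appendix 2), cycle lengths, median PFS of 5.5 months for Cohort C (Section 1.3.2.1), OS of about 20–24 months as a guide for Cohort C (Section 1.1.2), minimum follow-up of about 24 weeks (Section 6) and study length of about 4 years (Section 3.2).
- Assumed: 20% or 40% of patients would ever form ADA; median onset 0 to 180 days; median PFS of 3 months in A/B; median post-progression survival of 14 months (C) or 8 months (A/B); 15% of PFS events are deaths; treatment stops at progression; response is more likely with longer PFS; data cutoff at 24–72 or 24–208 weeks.

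Mean post-baseline samples, shortest against longest PFS quartile: 2.6 vs 5.5 in Cohort C and 1.6 vs 4.7 in A/B (2.6 vs 6.8 and 1.6 vs 5.5 with the longer follow-up).

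Apparent hazard ratio when the truth is 1.00:

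| Median ADA onset | C, PFS | C, OS | A/B, PFS | A/B, OS |
|---|---|---|---|---|
| 0–7 days | 0.96–0.98 | 0.91–0.97 | 0.93–0.95 | 0.86–0.93 |
| 21 days | 0.93–0.95 | 0.81–0.92 | 0.89–0.92 | 0.78–0.89 |
| 42 days | 0.87–0.90 | 0.70–0.87 | 0.84–0.88 | 0.69–0.83 |
| 84 days | 0.81–0.84 | 0.63–0.81 | 0.76–0.81 | 0.62–0.77 |
| 180 days | 0.74–0.80 | 0.58–0.76 | 0.70–0.77 | 0.59–0.73 |

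Apparent ORR, positive vs negative, runs from about 32% vs 31% (early onset) to about 40% vs 30% (late onset).

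**3. Sensitivity to the off-treatment samples.** These are separate runs with no ADA effect and the discontinuation sample taken.

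- 120-day sample obtained in 0–50% of patients and 30–80% of onsets by Week 12: PFS hazard ratio about 0.65–0.92. A second run on the same ranges gave 0.62–0.88.
- 120-day sample taken as scheduled: 0.76–0.96.
- As above, with at least 95% of onsets by Week 12: 0.98–1.01.

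Steps 2 and 3 together give roughly 0.65–0.98 for PFS.

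**4. What removes the bias.**

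- Only excluding patients with no post-baseline sample: at median onset of 42–180 days the ratios stay at 0.72–0.92 (PFS) and 0.61–0.90 (OS). If nearly all ADA appears before the first post-baseline sample, this exclusion alone gives 0.98–1.02.
- Landmark at week 9 (C) or week 8 (A/B), patients still at risk, clock restarted: PFS 0.99–1.01, OS 0.95–1.01.

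**The case against.** The strongest reply is that little depends on this. Section 6.7 makes the analysis optional and descriptive, Table 1 calls it exploratory, and Section 6.1 plans no formal testing. Section 6.7 also names no model and no clock, so the gap is an unspecified method more than a wrong one. All of that stands and limits the point to interpretation. It does not remove it: the section supplies one ADA status and permits its use in subgroups, and Section 6.4.2 starts PFS and OS at Cycle 1, Day 1.

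Noise is the second reply. Approximate 95% limits on a hazard ratio multiply and divide it by exp(1.96/√(d·p·(1 − p))). With p = 0.30 ADA positive (assumed), d = 40 events gives exp(1.96/√8.4) ≈ 2.0 and d = 85 gives exp(1.96/√17.85) ≈ 1.6. Much of the plausible bias is smaller than that. This is fair, but the bias is systematic and more patients would not reduce it.

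Three stronger readings are tempting, and the documents do not support them.

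- A reader might infer that the apparent PFS hazard ratio could be near 0.50. That appears only if the discontinuation sample, which Appendix 2 schedules for every patient, is dropped.
- A reader might infer that ADA will look protective whatever happens. The direction holds on average under no effect; with early onset the ratio is near 1, and a harmful effect would be reduced or masked, not necessarily reversed.
- A reader might infer that adverse events will look more frequent in ADA-positive patients. This was not computed. For events leading to discontinuation, which Section 6.5 summarises, early stopping means fewer samples and hence more negative status, so the direction could be the opposite.

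**Conclusion.** The point holds as an interpretive weakness in an optional, exploratory analysis. Applying the Section 6.7 status to efficacy from Cycle 1, Day 1 favours ADA-positive patients on average when ADA has no effect, through two routes: sampling tied to time on treatment, and no requirement for a post-baseline sample. The apparent PFS hazard ratio is roughly 0.65–0.98. The low end needs late onset and incomplete 120-day sampling; the high end corresponds to early onset. The documents give neither ADA onset times nor sample completeness, so this is a range under assumptions and not a forecast. A real loss of efficacy could be masked. The co-primary ORR and DCR analyses are untouched, ever/never status remains suitable for reporting incidence, and no direction is established for adverse events.

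**What to change.** Amend Section 6.7 as follows.

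- **Incidence:** keep ever/never status for this purpose only, and require at least one post-baseline ADA sample.
- **PFS and OS by ADA status:** classify from samples up to a fixed landmark about 8–9 weeks after the first atezolizumab dose, include only patients still at risk, and count time from the landmark. Existing sample times fit: Cycle 3, Day 1 in Cohort A (week 8) and Cycle 4, Day 1 in Cohort C (week 9). Cohort B starts atezolizumab on Cycle 1, Day 15, so its Cycle 3 and Cycle 4 samples fall 6 and 10 weeks after that dose; the text should name which one sets status. A time-dependent ADA covariate is an optional sensitivity analysis.
- **ORR by ADA status:** first scans are at 8 weeks ± 1 week (Section 4.4.5), so a week 8–9 landmark would discard or split first-scan responses. Use ADA status from samples before the first tumor assessment, for example Cycle 2, Day 1, or report ORR by ADA status with an explicit caveat.

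The cost is analysis-plan wording and modest programming, with no new samples or visits. The downside is that patients with events before the landmark leave this comparison and late-onset ADA is not captured as positive.
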